#### TAF/EVG Insert – Macaque Study

CONRAD study 2708 evaluated the PK of TAF and EVG following administration of vaginal inserts containing a combination of TAF/EVG in female pigtailed macaques. Vaginal inserts containing 10/8 mg, 10/16 mg or 40/24 mg of TAF/EVG were administered to groups of 4 female macaques. One insert was administered vaginally to each macaque 5 times over an 8-week period with at least 1 week between doses. Animals were dosed on a single occasion at the 24h PK interval and on two separate occasions for both 2 and 4h PK intervals. Plasma, vaginal fluid and vaginal tissue biopsy samples were collected at 0.5 (blood only), 2, 4 and 24 hours post-dose. These samples were analyzed for concentrations of TAF, TFV and EVG. Vaginal biopsies were also evaluated for TFV-DP concentrations. The TAF/EVG insert did not result in adverse behavioral changes, physical changes in the vaginal vault or measurable systemic exposure to TAF, TFV or EVG in the macaques. There was minimal dose proportionality between inserts for vaginal fluid or tissue concentrations. TFV and EVG in vaginal fluid after administration

of TAF/EVG (20/16 mg) showed the most favorable PK and resulted in TFV-DP and EVG tissue levels in range with those shown to provide in vivo protection against vaginal SHIV infection in macaques.

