## 9.1 Methods for Handling Missing and BLOQ Data

Each bioanalytical assay for blood, rectal fluid, rectal tissue, and cervicovaginal fluid has an assay sensitivity described by a lower limit of quantitation (LLOQ). These LLOQs will be reported for each matrix. Concentration values assayed below the LLOQ, as well as those classified as “Not Detected”, are identified as below the limit of quantitation (BLOQ).

In individual participant data listings, actual concentration values below the LLOQ will be displayed, if provided from the lab, along with the LLOQ for the assay. For values identified as BLOQ in the data, a listing will be provided displaying the assay and time point(s) of the BLOQ values.

Baseline samples that are BLOQ or missing will be assigned a numerical value of zero for the calculation of area under the concentration-time curve (AUC). Baseline samples that are missing will be excluded from the concentration summary calculations at baseline. Any anomalous quantifiable concentration values (at or above the LLOQ) observed at baseline will be identified in the study report and used for the computation of AUC.

Any other BLOQ concentrations that precede quantifiable samples in the initial portion of the profile or a BLOQ value that occurs between quantifiable data points, especially prior to  $C_{max}$ , will be evaluated to determine if an assigned concentration of zero makes sense, or if reanalysis or exclusion of the data is warranted. Following  $C_{max}$ , BLOQ values embedded between two quantifiable data points will be treated as missing when calculating AUC. If BLOQ values occur at the end of the collection interval (after the last quantifiable concentration), these will be treated as missing data. If consecutive BLOQ concentrations are followed by quantifiable concentrations in the terminal portion of the concentration curve, these quantified values will be excluded from the PK analysis by assigning them a value of missing, unless otherwise warranted by the concentration-time profile.

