Drug concentration-time data will be listed for each participant and summarized by descriptive statistics at each nominal collection time. BLOQ concentrations will be treated as zero for computation of descriptive statistics. Concentrations assigned a value of missing will be omitted from the calculation of descriptive statistics. If the calculated mean concentration is BLOQ, the mean value will be reported as BLOQ, and SD will be reported as ND (not determined). Median, quartiles, minimum and maximum may be reported, and if any of these values are BLOQ, they will be reported as BLOQ.

When a concentration of zero cannot be plotted, the concentration may be assigned the value of LLOQ divided by 2 so that it may be displayed.

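### SAP 9.1 drops some late quantified blood concentrations from the time-point summaries as well as from AUC and ke; limit the exclusion to the parameters and reconcile the zero/missing rule for trailing BLOQs

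*SAP*

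**What the plan says.** SAP 9.1 has a rule for profiles that reappear above the assay limit. "If consecutive BLOQ concentrations are followed by quantifiable concentrations in the terminal portion of the concentration curve", then "these quantified values will be excluded from the PK analysis by assigning them a value of missing", with the proviso "unless otherwise warranted by the concentration-time profile". The SAP does not say what would warrant an exception, who decides, or whether exclusions are counted.

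Three other sentences in SAP 9.1 interact with this rule:

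- For summaries: "Concentrations assigned a value of missing will be omitted from the calculation of descriptive statistics".
- Also for summaries: "BLOQ concentrations will be treated as zero for computation of descriptive statistics".
- For BLOQs at the end of a profile: "If BLOQ values occur at the end of the collection interval (after the last quantifiable concentration), these will be treated as missing data".

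A neighbouring rule is narrower. After Cmax, "BLOQ values embedded between two quantifiable data points will be treated as missing when calculating AUC". That one is confined to AUC. Anomalous quantifiable baseline values get the opposite default: they are reported and used in the AUC.

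The primary PK endpoints are concentrations (Protocol 10.2 as changed by Letter of Amendment 04; SAP 2.2). Protocol 10.7.2 describes them at every scheduled time, using the 1 to 72 h points. SAP 9.1 also lists concentration-time data for each participant.

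**The concern.** Removing an isolated late point is ordinary practice when fitting a terminal slope or computing an area. Here the removal takes effect by setting the value to missing, and a later sentence takes missing values out of the descriptive tables. A rule suited to cleaning parameters therefore reaches the observed concentrations, which are the primary endpoint.

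The handling is also lopsided. A participant who is BLOQ at 72 h can enter the summary as zero, while one who is quantified at 72 h after two BLOQs leaves it. In a first study of rectal dosing, whether drug is still found in blood at 24 to 72 h is part of the systemic PK objective. The plan could understate it, and a reader of the tables would see only a smaller n.

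**Working it through.** The documents give no figure that depends on this rule, so there is none to reproduce. They also give no LLOQs or expected human concentrations. Steps 2 to 4 therefore use assumed values in LLOQ units.

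**1. Which samples can the rule reach?** It needs two consecutive BLOQs and then a quantified value, in one participant within one dose. I enumerated every quantified/BLOQ pattern on the schedule in SAP section 9, Table 1.

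| Matrix | Samples per participant per dose | Times reachable after an earlier quantified value |
|---|---|---|
| Blood | 7 (1, 2, 4, 6, 24, 48, 72 h) | 6, 24, 48, 72 h |
| Rectal fluid, Group 1 | 3 (2, 6, 48 h) | none |
| Rectal fluid, Group 2 | 3 (4, 24, 72 h) | none |
| Rectal tissue and cell isolates | 2 (2, 48 h or 24, 72 h) | none |

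In rectal fluid the only possible pattern is BLOQ, BLOQ, quantified. The last value is then the peak, so it is doubtful that it belongs to a terminal portion. In tissue and cell isolates the pattern cannot occur.

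**2. Effect on a mean (assumed values).** Take N = 20 at 72 h in blood. Let k participants be quantified at r × LLOQ after two BLOQs, and the rest be BLOQ = 0. Keeping the values gives a mean of k × r / 20. Under the rule the mean is 0 on n = 20 − k.

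- k = 1, r = 1: 0.05 LLOQ against 0 (n = 19); share quantifiable 5% against 0%.
- k = 3, r = 2: 0.30 against 0 (n = 17); 15% against 0%.
- k = 5, r = 5: 1.25 against 0 (n = 15); 25% against 0%.

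When other participants are quantified throughout, the effect shrinks or turns:

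- 5 at 3 LLOQ plus 2 excluded at 2 LLOQ: (15 + 4)/20 = 0.95 kept, 15/18 = 0.83 excluded.
- 10 at 3 LLOQ plus 5 excluded at 2 LLOQ: (30 + 10)/20 = 2.00 kept, 30/15 = 2.00 excluded.
- 12 at 3 LLOQ plus 5 excluded at 2 LLOQ: (36 + 10)/20 = 2.30 kept, 36/15 = 2.40 excluded.

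**3. Effect near the LLOQ (assumed).** Suppose a flat level over 24, 48 and 72 h, independent log-normal errors with 30% CV, an earlier quantified value, and BLOQs kept as zero. Here σ = √ln(1 + 0.3²) = 0.294 and p = Φ(ln(level/LLOQ)/σ) is the chance that a sample is quantified. The share of quantified 72 h values deleted is (1 − p)². The share quantifiable afterwards is [p − p(1 − p)²] / [1 − p(1 − p)²].

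| Level / LLOQ | p | Share deleted | Share quantifiable, before → after |
|---|---|---|---|
| 0.8 | 0.224 | 60% | 22% → 10% |
| 1.0 | 0.50 | 25% | 50% → 0.375/0.875 = 43% |
| 1.2 | 0.733 | 7% | 73% → 72% |

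The SAP does not plan a detection percentage, so I simulated the planned summaries under the same model with N = 20.

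- At 0.8 × LLOQ the mean averages 0.27 LLOQ kept and 0.12 excluded. SAP 9.1 would print BLOQ either way. The maximum changes in about 60% of trials and becomes BLOQ in 15%. The median changes status in 0.1%.
- At 1.0 × LLOQ the mean is 0.64 against 0.55, printed as BLOQ both ways in 99% of trials. The median changes status in 18% and the maximum changes in about 25%.
- At 1.2 × LLOQ the mean is 1.03 against 1.01.

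**4. The trailing-BLOQ wording alters the direction.** If trailing BLOQs are missing in the summaries too, then in the model at the LLOQ the 50% of participants who are BLOQ at 72 h drop out, as do the 12.5% (0.5 × 0.25) who are quantified after two BLOQs. The remaining 37.5% are all quantified. The 72 h table would then show 100% quantifiable, against 50% with everything kept and 43% with BLOQ = 0. Also, once a late value is excluded, the BLOQs before it become trailing.

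**5. AUC.** Assume concentrations of 0, 20, 30 and 20 LLOQ at 0, 1, 2 and 4 h, C6 at 6 h, then BLOQ at 24 and 48 h. The linear-trapezoid area to 6 h is 10 + 25 + 50 + (20 + C6) = 105 + C6. Retaining a 72 h value with the embedded BLOQs treated as missing adds 33 × (C6 + C72).

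- C6 = 2, C72 = 1: 107 → 206, a factor of 1.9.
- C6 = 10, C72 = 5: 115 → 610, a factor of 5.3.

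Exclusion from AUC is therefore defensible.

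**The case against.** The strongest reply is that this is a narrow default. The exception can retain a coherent late profile, the individual concentrations are still listed, and a value that reappears after two BLOQs may be contamination, a swapped sample or assay error. Near the LLOQ the printed mean would usually read BLOQ whether or not the values are kept. All of this is fair, and it limits the size of the point. It does not remove it: the exception has no criterion, listings do not correct a table, and doubt about a value is a reason to flag it.

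Four stronger readings are tempting, but the documents do not support them.

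- **That real late drug is being deleted.** Nothing establishes whether such values would be drug or artefact.
- **That the whole primary PK endpoint is affected.** Step 1 shows that the clear reach is blood.
- **That the pattern is likely.** The macaque study reported no "measurable systemic exposure to TAF, TFV or EVG in the macaques", but its dosing was vaginal and its sampling ended at 24 h. In the rabbit study with rectal dosing (Protocol 2.6.2.1), plasma drug was measurable: mean Cmax was 2.42 to 8.31 ng/mL for EVG and 13.6 to 128 for TFV. Without LLOQs, closeness to the limit is an assumption.
- **That slowly formed TFV, BLOQ at 4 and 6 h and quantifiable at 24 h, would be deleted.** If nothing was quantified earlier, those BLOQs lie in the initial portion, and a different sentence in SAP 9.1 sends them for case-by-case evaluation. The deletion rule clearly applies only if an earlier value was quantified.

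A general claim of downward bias also fails, as steps 2 and 4 show.

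**Conclusion.** The point holds in limited form. By default, SAP 9.1 carries an exclusion suited to derived parameters into the by-time-point summaries that make up the primary PK analysis, and it conflicts with itself on whether trailing BLOQs are zero or missing. The effect is essentially confined to blood at 6 to 72 h.

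With BLOQs counted as zero, late detectability can be understated, mainly through n, the maximum, sometimes the median, and the plots. Under the assumed flat-level model the loss is 60%, 25% and 7% of quantified 72 h values at 0.8, 1.0 and 1.2 times the LLOQ. A true decline over 24 to 72 h would make two BLOQs followed by a quantified value rarer. These figures illustrate a range and do not predict this trial.

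The point is worth correcting because the change is nearly free; it does not threaten the study's conclusions.

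**What to change.** In SAP 9.1:

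1. Limit the exclusion of quantified values after consecutive BLOQs to AUC, ke and the parameters derived from them.
2. Keep every post-dose concentration at or above the LLOQ in the time-point tables and plots. Flag affected values in the listing and report how many were excluded from parameter calculation.
3. State the criterion for the remaining exception in the parameter calculations; it should not apply to the summaries.
4. State that trailing BLOQs are missing only for parameter calculation and are zero in descriptive summaries, so that the two parts of the section agree.

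The cost is a few sentences and one flag, with no new data. The downside is that an occasional contaminated or swapped sample stays in a summary, where the flag makes it visible.

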## 9.2 Primary PK Analyses

The primary PK analyses describe the concentrations of EVG, TAF, TFV, and TFV-DP in some or all of the following matrices: 1) blood, 2) rectal fluid (RF), 3) rectal mucosal tissue (RT) homogenates, and 4) rectal mucosal tissue cell isolates during each dosing regimen, one insert or two inserts. For each dosing regimen (one insert and two inserts), Table 2 below displays the drug concentrations to be analyzed for each PK specimen type.

Table 2: Expected PK Drug Concentrations per PK Specimen Type

PK Specimen Type	EVG	TAF	TFV	TFV-DP
Blood	X	X	X	
Rectal fluid	X	X	X	
Rectal tissue homogenates	X	X	X	
Rectal tissue cell isolates				X

NOTE: X=Drug concentrations expected.

As blood samples are collected among all participants at the enrollment visit and at seven post-dose time points per dose, RF samples are collected at three time points per dose for Group 1 participants and three separate time points per dose for Group 2 participants, and RT samples are collected at two time points per dose for Group 1 and two time points per dose for Group 2 participants, there are differences between how the concentration data for these matrices will be analyzed and summarized.

In general, due to the small number of concentrations available at sampling time points, a log transformation of the concentrations will be considered if the data suggest strong skewness. In this case, figures and tables will report medians with 95% C.I. at each sampling time point and figures will be presented on a semi-logarithmic scale (y-axis: logarithmic concentration; x-axis: linear time (h)). If no log

transformation of concentration is needed, then figures and tables will report the mean (with 95% confidence interval based on a Student's t-distribution approximation) at each sampling time point and figures will be presented on a linear scale.

### *Blood Concentrations*

For blood, EVG, TAF, and TFV concentrations can be plotted over time for each individual participant, and PK parameters (defined below) may be calculated for each participant and then summarized across all participants.

Displays of blood concentration data include:

- Tables summarizing the distribution of concentrations at each sampling time point for each dose administration (3 tables, one for each drug, with a column for each dose administration).
- Plots of individual participant concentration-time data presented in a panel for each dose administration (6 panels of plots (1 panel for each dose administration and drug)).
- Individual participant concentration-time data will also be overlaid on a single plot for each dose administration and drug (6 plots).
- Plots of mean/median concentration at each time point (with 95% C.I.) for each dose administration and drug (3 panels, one for each drug, with 2 plots (1 for each dose administration)).
- Listings of individual participant PK parameters for each dose administration and drug (6 listings).
- Tables summarizing the distributions of PK parameters across all participants for each dose administration and drug (6 tables).

### *Rectal Fluid and Rectal Tissue Concentrations*

For rectal fluid and rectal tissue, the concentration-time profile will consist of data from different participants at different sampling time points. Individual participant PK parameters will not be calculated for concentration data from rectal fluid and rectal tissue since data were not collected at each time point for each participant.

Displays of rectal fluid and rectal tissue concentration data include:

- For each matrix (RF, RT), tables summarizing the distribution of concentrations at each sampling time point for each dose administration and drug (7 tables (3 for RF, 4 for RT) with a column for each dose administration).
- For each matrix (RF, RT), scatter plots of drug concentration-time data for each dose administration (7 panels (3 for RF, 4 for RT) with 2 plots (1 for each dose administration)).
- For each matrix (RF, RT), plots of mean/median concentration at each time point (with IQR or 95% C.I., as appropriate) for each dose administration (7 panels (3 for RF, 4 for RT) with 2 plots (1 for each dose administration)).

The PK parameters are:

$C_{max}$	Maximum observed drug concentration.
$C_{last}$	Last observed drug concentration.
$t_{max}$	Time of occurrence for $C_{max}$
$AUC_{0-t}$	Area under the drug concentration-time curve to the time of the last measurable concentration.
$AUC_{0-\infty}$	Area under the drug concentration-time curve to infinite time. Equal to $AUC_{0-t}$ plus $AUC_{t-\infty}$ = $(C_{last} / k_e)$ .
$k_e$	Terminal elimination rate constant.

---

$t_{1/2}$	Half-life of drug elimination in the terminal phase.
%AUC ex	Percentage of AUC 0-∞ obtained by extrapolation, calculated as $[(C_{last} / k_e) / AUC_{0-∞} * 100]$

The time, in hours, to each sample collection time is calculated from the time of dose administration. The area under the curve (AUC) is calculated for each participant using the trapezoidal method from the time of dose administration to the time of the last sample collection (AUC0-t), typically at 72h.

Concentrations after  $C_{max}$  are used to determine the terminal elimination rate constant ( $k_e$ ) and associated half-life of drug elimination in the terminal phase ( $t_{1/2}$ ), when at least three such concentration values are available, according to the following formulas:

$$k_e = \ln(C_1/C_2) / (t_2 - t_1)$$

$$t_{1/2} = \ln(2) / k_e$$

where  $\ln$  is the natural logarithm,  $C_1$  is the first drug concentration value in the elimination phase after  $C_{max}$ ,  $C_2$  is the last drug concentration in the elimination phase after  $C_{max}$ , and  $t_1$  and  $t_2$  are the time (hours) of the first and last drug concentration values in the elimination phase after  $C_{max}$ , respectively, as measured from the time of dose administration.

The area under the blood drug concentration-time curve to infinite time (AUC0-∞) is calculated by extrapolating the area of the curve after the last observed blood drug concentration ( $C_{last}$ ) by dividing  $C_{last}$  by the terminal elimination rate constant ( $k_e$ ) and adding the result to AUC0-t. The percentage of AUC0-∞ obtained by extrapolation (%AUCex) is calculated as  $[(AUC_{t-∞} / AUC_{0-∞}) * 100]$ .

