## 9. PHARMACOKINETIC ANALYSES

Descriptive statistics will be used to summarize actual PK sample collection times (from dose administration) for blood, rectal fluid, rectal tissue, and cervicovaginal fluid samples, and these summaries will be provided by site and overall.

For each dosing regimen, blood samples are expected to be collected from all participants at baseline and at 1h, 2h, 4h, 6h, 24h, 48h, and 72h after dose administration. Samples of rectal fluid and cervicovaginal fluid (if applicable) are expected to be collected at the following study time points after dose administration: 2h, 4h, 6h, 24h, 48h, and 72h with samples collected for each participant only at specific time points based upon their group status (see table below). Similarly, samples of rectal tissue are expected to be collected at the following study time points after dose administration: 2h, 24h, 48h, and 72h with samples collected for each participant only at specific time points based upon their group status (see Table 1 below).

Table 1: Expected PK Sample Collection by Study Time Point

PK Specimen Type	Baseline Visit 2	1h, Visits 3 & 7	2h, Visits 3 & 7	4h, Visits 3 & 7	6h, Visits 3 & 7	24h, Visits 4 & 8	48h, Visits 5 & 9	72h, Visits 6 & 10
Blood	G12	G12	G12	G12	G12	G12	G12	G12
Rectal fluid			G1	G2	G1	G2	G1	G2
Rectal tissue			G1			G2	G1	G2
Cervicovaginal fluid			G1	G2	G1	G2	G1	G2

NOTE: G1=Group 1, G2=Group 2, G12=Groups 1 and 2.

A table summarizing the number and percentage of blood, rectal fluid, rectal tissue, and cervicovaginal fluid samples collected outside of the windows of the expected time points will be provided overall and by site. For samples collected outside of the window, a listing of sample collection times along with the amount of time before (-) the window or after (+) the window will be provided.

Allowable windows for the collection of blood, rectal fluid, rectal tissue, and cervicovaginal fluid are detailed in the MTN-039 SSP Manual in section 5.4.2 and Table 5-1 Sample Collection Time-Points Post-Insert Administration (and provided below).

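### The terminal rate constant rests on two concentrations and an undefined start of the elimination phase, so half-life and the extrapolated area depend on an unstated choice; AUC0-t also has two stated end points

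*SAP*

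**What the plan says.** The parameter definitions stand at the end of SAP section 9.2, after the rectal fluid and tissue displays, but individual parameters are planned for blood only.

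- **Rate constant.** ke = ln(C1/C2)/(t2 − t1) and t½ = ln(2)/ke. C1 "is the first drug concentration value in the elimination phase after" Cmax, and C2 "is the last drug concentration in the elimination phase after" Cmax. Concentrations after Cmax are to be used "when at least three such concentration values are available, according to the following formulas". The SAP gives no rule for when the elimination phase starts, no regression, no fit criterion and no limit on %AUCex.
- **Sampling.** SAP section 9: "blood samples are expected to be collected from all participants at baseline and at 1h, 2h, 4h, 6h, 24h, 48h, and 72h after dose administration".
- **AUC0-t.** The parameter table reads "Area under the drug concentration-time curve to the time of the last measurable concentration", and the abbreviation list in SAP section 1 agrees. The text below the table instead has AUC calculated "using the trapezoidal method from the time of dose administration to the time of the last sample collection", typically 72 h. Whether the trapezoids are linear or logarithmic is not stated.
- **AUC0-∞** is AUC0-t plus Clast/ke.
- **Trailing BLOQ values**, SAP section 9.1: "If BLOQ values occur at the end of the collection interval (after the last quantifiable concentration), these will be treated as missing data".

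**The concern.** The minimum-data rule asks for three values but the formula uses two, so the intermediate concentrations have no influence on the slope. Because the phase is undefined, the nearest operational instruction is that concentrations after Cmax are used. A programmer could therefore reasonably start at the first draw after the peak. If Cmax falls at 1 or 2 h, that is the 2 h or 4 h sample, which may still reflect distribution. The result would be an average slope over most of the profile, reported as terminal. Protocol section 10.7.2 itself describes the 1 to 72 h window as running only through initial elimination.

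At stake are t½, AUC0-∞ and %AUCex for blood. SAP section 9.2 says these may be calculated, but then plans six listings and six summary tables of them. This is the first rectal study of the insert (Protocol section 2.8.2), so these values could be carried into later development. Two analysts following the same text could report clearly different half-lives from the same data.

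**Working it through.** The plan states no value for ke, t½ or AUC, so there is no figure to reproduce. The check applies the SAP formulas to noise-free curves.

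**Inputs.** Sampling times and formulas come from SAP sections 9 and 9.2. The 8.7 h scenario uses the oral, ritonavir-boosted EVG half-life in Protocol section 2.7.2. Everything else is assumed: C(t) = 0.9·2^(−t/h_fast) + 0.1·2^(−t/h_slow), with Cmax observed at 1 h (so C1 at 2 h) or at 2 h (so C1 at 4 h).

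**1. Effect of where C1 is placed** (h_fast 2 h, h_slow 40 h; C(72) = 0.02872)

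| C1 at | C1 | ke | t½ |
|---|---|---|---|
| 2 h | 0.54659 | ln(0.54659/0.02872)/70 = 0.04209 | 16.5 h |
| 4 h | 0.31830 | ln(0.31830/0.02872)/68 = 0.03537 | 19.6 h |
| 6 h | 0.20263 | ln(0.20263/0.02872)/66 = 0.02960 | 23.4 h |
| 24 h | 0.06620 | ln(0.06620/0.02872)/48 = 0.01740 | 39.8 h |

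Log-linear regression on 24, 48 and 72 h also gives 39.8 h.

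Extrapolated area: 0.02872/0.04209 = 0.682 and 0.02872/0.03537 = 0.812, against a true tail of 1.657, so 41% and 49% of the truth. With the exact AUC0-t of 6.710, %AUCex is 0.682/7.392 = 9.2% or 0.812/7.522 = 10.8%, against 1.657/8.368 = 19.8%.

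**2. Other half-lives, C1 at 2 h and 4 h.** True 20 h (fast phase 2 h): 11.6 and 13.0 h. True 8.7 h (fast phase 1 h): 7.1 and 7.9 h; here %AUCex is 0.13 to 0.14% against 0.16%, which is immaterial.

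**3. Single phase.** If C(t) = C0·exp(−kt), any pair of points returns k, so there is no bias. One-compartment curves with a 4 h absorption half-life gave 24.6 h for a true 24 h, 9.0 for 8.7 and 5.4 for 5.0: 2 to 8% too long. There the first post-Cmax sample is the 24 h one, and regression gives the same values.

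**4. Precision** (constant error variance σ² on the log scale). The two-point slope has variance 2σ²/(t2 − t1)²; regression has σ²/Sxx.
- Points 2 to 72 h: Sxx = 4064, ratio 2·4064/70² = 1.66.
- Points 4 to 72 h: Sxx = 3372.8, ratio 2·3372.8/68² = 1.46.
- Points 24, 48, 72 h: Sxx = 1152, ratio 2·1152/48² = 1.00; the two slopes coincide.

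Using two points therefore costs precision, while the bias comes from where C1 sits.

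**5. Total AUC0-∞** (linear trapezoids, zero at baseline, C1 at 2 h). For 40 h: 6.997 + 0.682 = 7.679 against 8.368, 8% low. For 20 h: 5.582 + 0.138 = 5.720 against 5.482, 4% high. Using the curve's own time-zero value instead of zero, with C1 at 2 or 4 h, gives 1 to 2% low and 13 to 14% high. Over the 6 to 24 h gap alone, a linear trapezoid exceeds the log one by 17% at a half-life of 8.7 h and by 34% at 6 h.

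**6. AUC0-t end point** (assumed one-compartment curve, scale about 100, LLOQ 1). If trailing BLOQ values were counted as zero out to 72 h, one further triangle is added after the last quantifiable point:
- t½ 3 h: 296.5 + 27.78·18/2 = 546.5, up 84%.
- t½ 6 h: 925.2 + 6.579·24/2 = 1004.2, up 9%.
- t½ 8.7 h: 1357.6 + 2.261·24/2 = 1384.7, up 2%.

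Under SAP section 9.1 these values are missing and the triangle is not added.

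**The case against.** The strongest reply is that the SAP does not tell anyone to start at the first post-Cmax sample. It restricts both points to the elimination phase, and a pharmacologist who starts at 24 h gets the regression answer exactly (step 4). That stands: a reader might infer that the SAP prescribes mixing distribution with elimination, but the text only permits it by leaving the phase undefined.

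A reader might also infer that AUC0-∞ is biased low. The documents do not support that. Only the extrapolated part is low when ke is too high, and the unstated trapezoid rule can outweigh it; the total went both ways in step 5.

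The large half-life errors rest on assumed curves. With the one half-life taken from the protocol, the shortfall is about 1 h and the extrapolated area is negligible. Multi-phase decline is plausible, since TFV in plasma is formed from a short-lived prodrug, but no human rectal data settle it.

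Finally, the primary PK endpoints are concentrations, PK is descriptive without formal testing (SAP section 2.5), and the BLOQ rule largely settles AUC0-t. For TAF, if plasma is BLOQ by about 5 h as after oral dosing (Protocol section 2.7.2), a 1 h peak leaves only the 2 h and 4 h values, so the three-value rule means ke is not computed. All of this limits the severity. It does not remove the ambiguity in ke or the unused data.

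**Conclusion.** The point holds as a moderate one. SAP section 9.2 requires three post-Cmax values, uses two, and does not define the phase from which they come. On one assumed biexponential curve the wording admits half-lives from 16.5 to 39.8 h for a true 40 h. Starting at 2 or 4 h gives 16.5 to 19.6 h and an extrapolated area of 41 to 49% of the truth; for an assumed 8.7 h the same starts give 7.1 to 7.9 h. These errors require a decline with more than one phase. With one phase there is no bias, and with slow absorption the half-life is slightly long. Independently of bias, a two-point slope from 2 or 4 h has about 1.5 to 1.7 times the variance of regression on all the points.

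No direction of error in total AUC0-∞ is established. The AUC0-t contradiction is real wording with little practical effect if SAP section 9.1 is followed. No test and no primary concentration summary depends on ke.

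**What to change.** In SAP section 9.2:

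- Estimate ke by log-linear regression on at least three quantifiable terminal-phase points after Cmax. Prespecify how the points are chosen (for example, the last three, extended backwards only while adjusted R² does not fall) and a minimum fit. The documents give no thresholds, so the team must set them.
- Flag t½ and AUC0-∞, or do not report them, when the fit is poor or %AUCex exceeds a stated limit.
- Define AUC0-t once, to the last quantifiable concentration, in line with SAP section 9.1.
- State the trapezoid rule, for example linear while rising and logarithmic while falling.

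The cost is SAP wording and some participants without a reportable half-life; no new samples are needed. Regression does not rescue a tail lost to the assay limit. On an assumed curve (90% with a 2 h and 10% with an 8.7 h half-life, absorption half-life 0.25 h, scale 100, LLOQ 1), the last three quantifiable points are 4, 6 and 24 h. They give 4.8 h against 4.3 h from two points, so the flags are needed as well as the regression.
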